Much of the improvement in the median overall survival in multiple myeloma (MM) is owed to incorporation of proteasome inhibitors (PIs) and immunomodulators into the contemporary combination regimens. However, despite high remission rates in combination regimens, PI-based therapy faced limitation in both intrinsic and acquired PI resistance. Moreover, patients are currently treated empirically as no markers of PI sensitivity have been identified. Resting on novel pre-clinical observations from studying previously established MM cell lines with bortezomib and carfilzomib resistance, we identified *MUC20* expression as a viable biomarker modulating the intrinsic PI-sensitivity and/or relative resistance to PIs. In the currently proposed phase I/II study, we aim to treat patients with relapsed and/or relapsed refractory MM who have previously progressed on carfilzomib with an FDA approved c-MET inhibitor, *cabozantinib*. Our hypothesis is that the additional rescue blockade with cabozantinib added to the carfilzomib will (1) be safe and tolerable and (2) will show activity by demonstrating objective response to combination carfilzomib/cabozantinib therapy. In correlative studies, we aim to show that (1) the serum and marrow MUC20 levels which will be judged by genomic and flow cytometric studies will directly correlate with primary plasma cell MUC20/c-Met pathway activation and inversely correlate with PI resistance; and (2) a correlation of the gene and MUC20 expression profiles of patients with clinical outcomes may confirm the biomarker MUC20 as a predictor of disease sensitivity to PI, and allow future personalization of c-Met-targeted therapies, as well as combination approaches based on c-Met inhibitors.

SCHEMA

PROTOCOL THERAPY: 28-day Cycles

Cabozantinib:

Phase I: Level -1 = 20 mg or Level 0 = 40 mg or Level +1 = 60 mg, PO daily on days 1-28
Phase II: One of phase I dosing levels identified as MTD, PO daily on days 1-28

Carfilzomib: 27 mg/m² IV over 10 min on days 1, 2, 8, 9, 15, 16

Dexamethasone: 40 mg PO/IV on days 1, 8, 15 and 22
(for patient age ≥ 75, acceptable to be given as 20 mg per week PO/IV)

TABLE OF CONTENTS		Page
Abstract		3
Schema		4
TABLE OF CONTENTS		5
1. Objectives		7
2. Background		8
3. Eligibility		23
4. Registration Procedures		29
5. Treatment Plan		31
6. Measurement of Effect		54
7. Study Calendar and Assessments		57
8. Drug Formulation and Procurement		58
9. Toxicity and Adverse Events Guidelines		64

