
2.4 RATIONALE FOR TARGETING c-MET IN CARFILZOMIB RESISTANT MULTIPLE MYELOMA

Multiple myeloma (MM) is a hematologic malignancy of monoclonal plasma cells and it remains incurable despite rapidly progressive armamentarium of therapeutic agents. Much of the improvement in the median overall survival in patients with MM is owed to incorporation of proteasome inhibitors (PIs)⁴⁶ and immunomodulators (IMiDs)^{47,48} into the contemporary combination regimens.

Bortezomib is the first PI to gain regulatory approval when it became available as a single agent in the relapsed and/or refractory setting based on data from series of phase I through III trials¹⁹⁻²¹, and was subsequently approved as part of front-line therapy with melphalan and prednisone¹⁰. Despite high remission rates in combination regimens, bortezomib-based therapy faced limitation in both intrinsic and acquired bortezomib resistance⁴⁹. Mutation and overexpression of the proteasome subunit PSMB5 (proteasome subunit β type 5) have been demonstrated to be an important mechanism of bortezomib resistance^{50,51}. Other causative factors play a role in development of proteasome resistance including persistent implication of NF- κ B signaling pathways in *in vitro* and *in vivo* studies⁵², antioxidant signaling in MM patient samples as well as MM cell lines^{53,54} as well as bone marrow microenvironment with IGFs (insulin-like growth factors)^{55,56} and Btk (Bruton's tyrosine kinase) pathway⁵⁷.

[figure not shown]
A more durable inhibition of the proteasome compared to reversible effect of bortezomib is achieved with second generation proteasome inhibitor Carfilzomib (Kyprolis), which is a peptide epoxy-ketone that binds the N-terminal threonine active site of the β 5 subunit of the proteasome in an irreversible manner^{58,59}. The efficacy of single-agent carfilzomib in patients with disease refractory to bortezomib and IMiD therapy was established in the PX-171-003-A1 study, a multicenter single-arm phase II trial, with an overall response rate of 24%, and the median duration of response of 7.8 months⁶⁰. In a phase II trial (PX-171-004) of bortezomib naïve patients, the response rate with single-agent carfilzomib was approximately 50%⁶¹. Importantly, in the process of emergence of PI resistance that is poorly understood, even though carfilzomib shows activity in bortezomib resistant multiple myeloma cell lines and patient samples⁶², resistance inevitably emerges to carfilzomib as well.

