4. Patients eligible for this trial will be those who have previously failed carfilzomib at any point either as a single agent, or carfilzomib in combination with dexamethasone, or carfilzomib in combination with dexamethasone and any of the following agents: revlimid, cyclophosphamide, pomalidomide, daratumumab or bendamustine. Given the potential for compounding/worsening toxicities with the addition of cabozantinib to carfilzomib, patients eligible for the trial will have to have had very good tolerance to carfilzomib in the context of described regimens, with resolved prior toxicity to grade 1 or better, and **no toxicities due to carfilzomib that required dose reductions to less than 27 mg/m^2** .
5. Patients must have disease that has relapsed after carfilzomib therapy, with progressive disease (PD) being defined as an increase of 25% from the lowest response value in any one or more of the following:
 - ❖ Serum M-component (the absolute increase must be $\geq 0.5 \text{ g/dL}$) **and/or**
 - ❖ Urine M-component (the absolute increase must be $\geq 200 \text{ mg/24 hours}$) **and/or**

- ❖ Only in patients without a measurable serum and urine M protein level: the difference between involved and uninvolved FLC levels (absolute increase) must be >10 mg/dL
- ❖ Definite development of new bone lesions or soft tissue plasmacytomas or definite increase in the size of existing bone lesions or soft tissue plasmacytomas
- ❖ Development of hypercalcemia (corrected serum calcium >11.5 mg/dL) that can be attributed solely to the plasma cell proliferative disorder

Patients with relapsed disease will be considered to be those who have had progression, as defined above, off of any therapy, and who completed their therapy more than 60 days prior to the finding of progression. Patients with relapsed and refractory disease will be considered to be those who have had progression, as defined above, while still on their last line of therapy, or who progressed within 60 days of finishing their most recent therapy.

6. Patients must have completed their most recent drug therapy directed at multiple myeloma in the following timeframes:

- ❖ Chemotherapy, biological therapy, immunotherapy, monoclonal antibody or an investigational therapy at least 3 weeks prior to starting cabozantinib
- ❖ Corticosteroids at least 3 weeks prior to starting cabozantinib, except for a dose equivalent to dexamethasone of ≤4 mg/day

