10.4 Stopping Rules

A response rate of 5% or less will be considered as clinically insignificant, while a response rate of 25% will be considered as clinically significant. With alpha= 0.05 and power of 0.80, the Simon optimal 2-stage design requires minimum enrollment of 9 patients in the first stage. The hypothesis will be rejected and enrollment will cease if no response is seen in the 9 patients. If at least 1 response is seen in the first 9 patients, another 14 patients will be accrued, for a total of 17 evaluable patients. At the end of the trial, the drug will be rejected if no more than 2 responses are seen in the total of 17 evaluable patients.

Cabozantinib will be taken in 20-mg capsules to reach the target dose levels as determined during the phase I and phase II portions of the study. This therapy will be continued without a cap on the number of allowed cycles, unless one of the following occurs:

- ❖ Disease progression after two cycles or later of therapy
- ❖ Intercurrent illness that prevents further administration of treatment
- ❖ Unacceptable adverse event(s)
- ❖ Patient decides to withdraw from the study
- ❖ General or specific changes in the patient's condition render the patient unacceptable for further treatment in the judgment of the investigator
- ❖ Patient becomes pregnant
- ❖ Patient loses the ability to freely provide consent through imprisonment or involuntary incarceration for treatment of a psychiatric or physical illness
- ❖ Patient achieves complete remission (CR), and the patient and investigator feel that discontinuation of cabozantinib is in the patient's best interests, or

- ❖ Patient achieves a level of response that qualifies him or her for another therapy, such as high dose therapy with autologous stem cell transplantation.

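### Entry criteria leave carfilzomib failure undefined and tie refractoriness to the last line, so the 5% null is not a secure background rate for crediting cabozantinib

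*Combined protocol and SAP*

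**What the plan says.** **Operative criteria.** Section 3.1 item 4 reads: "Patients eligible for this trial will be those who have previously failed carfilzomib at any point". It lists qualifying regimens but does not say what counts as failure. Item 5 adds: "Patients must have disease that has relapsed after carfilzomib therapy". It then defines two groups and excludes neither:

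- Relapsed: progression "off of any therapy, and who completed their therapy more than 60 days prior to the finding of progression".
- Relapsed and refractory: progression "while still on their last line of therapy, or who progressed within 60 days of finishing their most recent therapy". This line need not contain carfilzomib.

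Appendix A, the checklist completed before registration (section 4.2), repeats both items.

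**Population as described elsewhere.** The abstract speaks of "relapsed and/or relapsed refractory MM who have previously progressed on carfilzomib". Sections 1.1, 4.1 and 12.4 describe relapsed and refractory patients who have lost response to carfilzomib. The central clinical hypothesis in section 2.5 concerns patients who have become resistant to it. The title, as given in Appendix A, is about reversing that resistance.

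**Treatment and test.** Every patient receives carfilzomib again (schema, section 8.2.4), with dexamethasone in the schema, and there is no control arm. Sections 10.1 and 10.4 specify a Simon two-stage design of 5% against 25%: stop at 0 responses in 9, and reject the drug at 2 or fewer in 17. The reason given for the null is "A response rate of 5% or less will be considered as clinically insignificant". Section 10.7.2 rests all conclusions on all eligible patients. No analysis by carfilzomib refractoriness is planned.

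**The concern.** The criteria do not establish that each patient's disease is refractory to carfilzomib. Two kinds of patient show the gap:

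1. One responded to carfilzomib, stopped, and relapsed untreated a year later.
2. One responded to carfilzomib several lines ago, relapsed off it, and has just progressed on a different drug. Item 5 labels this patient relapsed and refractory, although the refractoriness was to something else.

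Both can enter if relapse after stopping carfilzomib counts as having failed it. Item 5 invites that reading and item 4 does not rule it out.

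Both restart carfilzomib in this trial. If some such patients respond to carfilzomib and dexamethasone alone, those responses count exactly as a response that cabozantinib made possible. The go/no-go rule could then be met with no contribution from cabozantinib. The overall ORR would not show whether the responders were the resistant patients whom the rationale is about.

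**Working it through.** **Inputs from the plan** (sections 10.1 and 10.4): null 0.05, alternative 0.25, 9 patients in stage 1 (stop at 0 responses), 17 evaluable in total, success at 3 or more responses.

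**Step 1: reproduce the stated design.** With X₁ the responses among the first 9,

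P(success) = Σ from x = 1 to 9 of P(X₁ = x) × P(Bin(8, p) ≥ 3 − x).

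At p = 0.05:

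- x = 1: 0.2985 × 0.0572 = 0.0171
- x = 2: 0.0629 × 0.3366 = 0.0212
- x ≥ 3: 0.0084
- Sum: 0.047

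At p = 0.25 the same formula gives 0.812. An exhaustive search over designs up to 30 patients confirms that 0/9, 2/17 is the Simon optimal design. The plan's own figures hold.

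**Step 2: dependence on the background rate.** Put other values of p through the same rule, taking p as the response rate to carfilzomib and dexamethasone alone in the enrolled mix:

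| Background rate | P(success) with no cabozantinib effect |
|---|---|
| 5% | 4.7% |
| 6% | 7.3% |
| 8% | 14% |
| 10% | 22% |
| 15% | 46% |

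**Step 3: sensitivity to the enrolled mix.** Let f be the share of patients not refractory to carfilzomib and q their response rate to re-treatment without any cabozantinib effect. Assume that refractory patients respond at 5%. Then p = 0.05(1 − f) + qf. For example, f = 0.2 and q = 0.15 give p = 0.04 + 0.03 = 0.07, and P(success) = 10.4%.

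| q | f = 10% | f = 20% | f = 30% | f = 50% |
|---|---|---|---|---|
| 10% | 6% | 7% | 9% | 12% |
| 15% | 7% | 10% | 14% | 22% |
| 24% | 10% | 17% | 26% | 43% |

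**Status of the assumptions.** The documents give neither f nor q. Section 2.4 reports single-agent carfilzomib "with an overall response rate of 24%, and the median duration of response of 7.8 months", but in patients refractory to bortezomib and an immunomodulator. That is not a re-treatment rate, and it serves here only as an upper anchor. The rows for 10% and 15% do not depend on it. All figures use the 17-patient total. Sections 10.1 and 10.4 also speak of 14 further patients after the first 9, which does not fit 17; that is a separate matter.

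**The case against.** **The criteria do ask for failure.** Item 4 requires it, and the phrase about timing can be read as allowing any earlier line rather than waiving failure. On a strict reading the first example patient never failed carfilzomib. Sections 1.1, 4.1 and 12.4 also describe relapsed and refractory disease. This stands in part: the fault is an undefined term and passages that disagree, not the absence of any requirement. A reader might infer that the criteria do not select for resistance at all, and the text does not support that. Equally, nothing in the criteria or the checklist imposes the strict reading, and the abstract's and/or wording contemplates relapsed-only disease.

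**The test is not about reversal.** Section 1.1 aims to estimate ORR, section 10.2 reports it with a 95% confidence interval, and section 10.4 presents 5% as a threshold of clinical interest, not a re-treatment benchmark. If the true ORR were 14.5%, rejecting 5% would be correct. This stands. A reader might call the 10–43% range an inflated false-positive rate, but it is not type I error of the stated test. It is the chance of crediting cabozantinib when cabozantinib did nothing.

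**Stricter entry would not prove reversal.** Even in strictly refractory patients, dexamethasone or cabozantinib's own activity could produce responses. This stands too. Stricter entry would make 5% a more credible background rate, and no more. The paired baseline and post-cycle-2 marker studies in section 5.8 offer some indirect evidence, but section 5.8.4 says that they may not be run if no clinical response is seen.

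**Broad entry is defensible in early phase.** Agreed, provided that the result can be read by refractory status. At present no such reading is planned.

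**Conclusion.** The point holds as a gap between the entry criteria and the population that the title and hypothesis describe. Patients not shown to be carfilzomib-refractory can enrol, and their responses to re-treatment count toward success. The 5% null is therefore not a secure background rate for attributing responses to cabozantinib.

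The size depends on two quantities that the documents do not give. Across the ranges tried, the chance of passing with no cabozantinib effect is 6% to 43%, against 4.7% when every patient is refractory and responds at 5%. At the milder end (q of 10–15%, f of 10–20%) it is 6–10%.

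The stated design and the ORR estimate are not wrong in themselves. What is weakened is the step from a positive result to a statement about cabozantinib or about resistance. It should be fixed, but it does not invalidate the trial.

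**What to change.** 1. **Reconcile the population.** The sponsor should decide which population is intended, define carfilzomib failure, and bring the abstract and sections 1.1, 2.5, 4.1 and 12.4 into line with section 3.1 items 4 and 5 and Appendix A. Narrowing entry is the sponsor's choice and may slow accrual.
2. **Record status at registration, whatever entry rule is kept.** Add two fields: carfilzomib-refractory yes/no, applying the protocol's own 60-day definition to the last carfilzomib-containing regimen, and the carfilzomib-free interval. Section 5.2.1 already takes prior regimens at screening. The same variable would serve the hypothesis in section 5.8 relating MUC20 to proteasome-inhibitor resistance.
3. **Pre-specify the reading in 10.1 and 10.2.** Report ORR with a 95% confidence interval separately by carfilzomib-refractory status. State that any claim about overcoming carfilzomib resistance rests on the refractory group, and describe it as supportive rather than proof because the trial is single-arm.

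The cost of items 2 and 3 is two case report form fields and one table, with no effect on accrual. The drawback is that fewer than 17 patients may stand behind the resistance statement, so its interval will be wide.

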3.2 EXCLUSION CRITERIA

1. Patients who are receiving any concurrent investigational agent with known or suspected activity against multiple myeloma, or those whose adverse events due to agents administered more than 4 weeks earlier have not recovered to a severity of grade 0 or grade 1.
2. Patients who have known central nervous system involvement with multiple myeloma will be excluded from this clinical trial because of their poor prognosis and because they often develop progressive neurologic dysfunction that would confound the evaluation of neurologic and other adverse events.
3. Patients who have previously been treated with another agent targeting the *MUC20/c-Met* axis, including either monoclonal antibodies to *MUC20* or c-Met, or small molecule inhibitors of c-Met.
4. Patients with a known history of allergic reactions attributed to compounds of similar chemical or biologic composition to cabozantinib.
5. Cabozantinib is metabolized by CYP3A4. The metabolism and consequently overall pharmacokinetics of cabozantinib could be altered by inhibitors and/or inducers or other substrates of CYP3A4. It is recommended that chronic concomitant treatment with strong

CYP3A4 inhibitors (eg, phenytoin, carbamazepine, rifampin, rifabutin, rifapentine, phenobarbital, and St. John's Wort) or inducers should be avoided because it may significantly decrease cabozantinib concentrations. If patients are taking any strong CYP3A4 inhibitors, alternate medications with no or minimal CYP3A4 inhibitors should be sought prior to trial enrolment. While mild inhibitors/inducers of these cytochrome P450 isoenzymes are not specifically excluded, investigators should be aware that cabozantinib exposure may be altered by the concomitant administration of these drugs, and avoidance is also recommended. Lists including medications and substances known or with the potential to interact with CYP3A4 are provided in Appendix G.

6. Uncontrolled or ongoing/active infection. Due to side effect profile of cabozantinib, patients with the following history will also not be eligible for the trial: patients with a recent history of hemorrhage or hemoptysis; patients with dehiscence or wound healing complications requiring medical intervention; patients with severe hypertension that cannot be controlled (blood pressure of > 150 systolic or > 100 diastolic mmHg) with anti-hypertensive therapy within 7 days of first dose of therapy.
7. Pregnant or lactating women are excluded from this study because cabozantinib is a tyrosine kinase inhibitor with the potential for teratogenic or abortifacient effects. Because there is an unknown but potential risk for adverse events in nursing infants secondary to treatment of the mother with cabozantinib, breastfeeding should be discontinued if the mother is treated with cabozantinib.
8. Patients with non-secretory multiple myeloma, active plasma cell leukemia, defined as either having 20% of peripheral white blood cells comprised of CD138⁺ plasma cells, or an absolute plasma cell count of $2 \times 10^9/L$, known amyloidosis, or known POEMS syndrome (plasma cell dyscrasia with polyneuropathy, organomegaly, endocrinopathy, monoclonal protein, and skin changes)
9. Patients who have required plasmapheresis and exchange less than 2 weeks prior to initiation of therapy with cabozantinib
10. Patients with known moderate or severe hepatic impairment, active hepatitis A, B, and/or C infection, due to the difficulty that would be faced in assessing the attribution of any events of hepatic toxicity while on cabozantinib therapy.
11. Patients with a "currently active" second malignancy, other than non-melanoma skin cancer and carcinoma in situ of the cervix, should not be enrolled. Patients are not considered to have a "currently active" malignancy if they have completed therapy for a prior malignancy, are disease free from prior malignancies for >5 years, and are considered by their physician to be at less than 30% risk of relapse. In addition, patients with basal cell carcinoma of the skin, superficial carcinoma of the bladder, carcinoma of the prostate with a current PSA value of <0.5 ng/mL, or cervical intraepithelial neoplasia will be eligible. Finally, patients who are on hormonal therapy for a history of either prostate cancer or breast cancer may enroll, if there has been no evidence of disease progression during the previous three years.
12. Allergy to carfilzomib or cabozantinib or any excipients
13. Uncontrolled intercurrent illness including medical, psychiatric, cognitive or other conditions, psychiatric illness/social situations that would compromise the patient's ability to understand the patient information, to give informed consent, to comply with the study protocol or to complete the

study or, in the judgment of the Principal Investigator, would make the patient inappropriate for study participation.

14. The subject has experienced any of the following:

- ❖ clinically-significant GI bleeding within 6 months before the first dose of study treatment;
- ❖ GI disorders particularly those associated with a high risk of perforation or fistula formation including:
 - Tumors invading the GI tract, active peptic ulcer disease, inflammatory bowel disease (eg, Crohn's disease), diverticulitis, cholecystitis, symptomatic cholangitis or appendicitis, acute pancreatitis or acute obstruction of the pancreatic duct or common bile duct, or gastric outlet obstruction
 - Abdominal fistula, GI perforation, bowel obstruction, intra-abdominal abscess within 6 months before randomization,

Note: Complete healing of an intra-abdominal abscess must be confirmed prior to randomization

- ❖ hemoptysis of ≥ 0.5 teaspoon (2.5ml) of red blood within 3 months before the first dose of study treatment;
- ❖ any other signs indicative of pulmonary hemorrhage within 3 months before the first dose of study treatment.
- ❖ Patient who have developed or have had history of pulmonary hemorrhage while on carfilzomib will be excluded (fatal pulmonary hemorrhage has been observed with carfilzomib).

15. The subject has radiographic evidence of cavitating pulmonary lesion(s);

16. The subject has tumor invading or encasing any major blood vessels;

17. The subject has evidence of tumor invading the GI tract (esophagus, stomach, small or large bowel, rectum or anus), or any evidence of endotracheal or endobronchial tumor within 28 days before the first dose of cabozantinib;

18. Corrected QT interval calculated by the Fridericia formula (QTcF) > 500 ms per electrocardiogram (ECG) within 14 days before first dose of study treatment *Note: If a single ECG shows a QTcF with an absolute value > 500 ms, two additional ECGs at intervals of approximately 3 min must be performed within 30 min after the initial ECG, and the average of these three consecutive results for QTcF will be used to determine eligibility.*

19. Inability to swallow intact tablets

20. The subject has prothrombin time (PT)/INR or partial thromboplastin time (PTT) test $\geq 1.3 \times$ the laboratory ULN within 7 days before the first dose of study treatment;

21. Concomitant anticoagulation at therapeutic doses with oral anticoagulants (eg, warfarin, direct thrombin and Factor Xa inhibitors) or platelet inhibitors (eg, clopidogrel);

Note: Low-dose aspirin for cardioprotection (per local applicable guidelines), low-dose warfarin (< 1 mg/day), and low dose, low molecular weight heparins (LMWH) are permitted if started > 6 months prior to randomization. LMWH used as therapeutic anticoagulation may increase observed PTT levels in subjects. Anticoagulation with therapeutic doses of LMWH is allowed in subjects without radiographic evidence of brain metastasis, who are on a stable dose of LMWH for at least

24 weeks before randomization, and who have had no complications from a thromboembolic event or the anticoagulation regimen.

22. Subjects who have Carfilzomib-related posterior reversible encephalopathy syndrome (PRES) and thrombotic microangiopathy (TMA) should not be challenged with Carfilzomib.

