- ❖ Nitrosoureas, nitrogen mustards, mitomycin C, at least 6 weeks prior to starting cabozantinib
- ❖ Autologous stem cell transplantation or autologous chimeric antigen receptor (CAR) T cell therapy at least 12 weeks prior to starting cabozantinib
- ❖ Allogeneic stem cell transplantation or allogeneic CAR T cell at least 24 weeks prior to starting cabozantinib, and these patients must also not have moderate to severe active acute or chronic graft versus host disease

7. Patients must be age 19 or older (state of Nebraska), because no dosing or adverse event data are currently available on the use of cabozantinib in patients <19 years of age.

8. Eastern Cooperative Oncology Group (ECOG) performance status of 0, 1, or 2; please see Appendix E)

9. Patients must have evidence of adequate bone marrow reserves, as defined by the following:

- ❖ Absolute neutrophil count (ANC) $\geq 1,000$ cells/mm³ without growth factors within 1 week of the initiation of treatment
- ❖ Total white blood cell count (WBC) $\geq 2,000$ cells/mm³ without growth factors within 1 week of the initiation of treatment
- ❖ Hemoglobin ≥ 8 g/dL without red blood cell transfusions within 2 weeks of the initiation of treatment
- ❖ Platelet counts of $\geq 100,000$ cells/mm³ for patients who have bone marrow plasmacytosis of <50%, or platelets $\geq 50,000$ cells/mm³ for patients who have bone marrow plasmacytosis of $\geq 50\%$

10. Patients must have evidence of adequate hepatic function, as defined by the following:

- ❖ Total bilirubin ≤ 1.5 times the upper limit of the institutional normal values
- ❖ Total AST (SGOT) and ALT (SGPT) ≤ 2.5 times the upper limit of the institutional normal values

11. Patients must have evidence of adequate renal function, as defined by the following:

- ❖ Serum creatinine within the institutional normal limits, OR if the creatinine is elevated

- ❖ Creatinine clearance (CrCl) ≥ 30 mL/min., as measured by a 24-hour urine collection, or estimated by the Cockcroft and Gault formula:

$$\text{Female CrCl} = \frac{(140 - \text{age in years}) \times \text{weight in kg} \times 0.85}{72 \times \text{serum creatinine in mg/dL}}$$

$$\text{Male CrCl} = \frac{(140 - \text{age in years}) \times \text{weight in kg} \times 1.00}{72 \times \text{serum creatinine in mg/dL}}$$

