5.7. DOSING DELAYS / DOSE MODIFICATIONS

In Phase I of this study we will determine the MTD among three doses. DLTs will be based solely on adverse events that occur during cycle 1. The definition of DLT includes:

- a. Any non-hematological toxicity Grade ≥ 3 , except for alopecia and nausea uncontrolled by medical management.
- b. Grade 4 neutropenia lasting more than 5 days.
- c. Febrile neutropenia of any duration (ANC $<1.0 \times 10^9/L$ fever $\geq 38.5^{\circ}\text{C}$)
- d. Grade 4 thrombocytopenia, or Grade 3 thrombocytopenia with bleeding, or any requirement for platelet transfusion
- e. Grade 4 anemia, unexplained by underlying disease.

We will study three dose levels using the 3+3 algorithm, so that we will accrue a minimum of 3 patients and a maximum of 18 patients in Phase I. The initial dose of cabozantinib for all patients treated on this study will be 20 mg P.O. daily, which is designated dose level -1. In the event that dose modifications are needed for toxicities, the following additional dose levels will be used:

Dose Level	Cabozantinib Dose
-1	20 mg p.o., daily
0	40 mg p.o., daily
+1	60 mg p.o., daily

To allow for optimal experimental design, capped dose of carfilzomib of 27 mg/m^2 will be used in the study without dose escalations or de-escalations. Given the potential for compounding/worsening toxicities with the addition of cabozantinib to carfilzomib, patients eligible for the trial will have to have had very good tolerance to carfilzomib in the context of treatment regimens they were receiving, with resolved prior carfilzomib toxicities to grade 1 or better, and no toxicities due to carfilzomib that required dose reductions to less than 27 mg/m^2 as dose adjustments will be allowed in the cabozantinib only. Stopping of carfilzomib however will be allowed if the adverse events secondary to carfilzomib that require its stopping are observed/met.

Specific dose modifications guidelines will be followed for the adverse events nausea, vomiting, diarrhea, neutropenia, and thrombocytopenia, and are detailed below. If a patient experiences several adverse events and there are conflicting recommendations, the investigator should use the recommended dose adjustment that reduces the dose to the lowest level.

Event Name	Diarrhea
Grade of Event	Management/Next Dose for Cabozantinib
\leq Grade 1	No change in dose
Grade 2	Hold until \leq Grade 1. Resume at same dose level.

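### Entry rules leave a one-week gap in toxicity recovery and set no transfusion-free window for platelets, while section 5.7 counts any cycle 1 platelet transfusion as a DLT and section 10.1 does not

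*Combined protocol and SAP*

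**What the plan says.** **Recovery from earlier toxicity.** Exclusion 1 in section 3.2, repeated in Appendix A, bars "those whose adverse events due to agents administered more than 4 weeks earlier have not recovered" to grade 0-1. Inclusion 6 in section 3.1 sets the washout for most systemic treatment: "Chemotherapy, biological therapy, immunotherapy, monoclonal antibody or an investigational therapy at least 3 weeks prior to starting cabozantinib". Some therapies have longer intervals of 6, 12 or 24 weeks.

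Inclusion 4 adds a recovery condition without a time limit, "with resolved prior toxicity to grade 1 or better", inside a sentence about tolerance of carfilzomib in the listed regimens. Section 5.7 restates it more narrowly: "with resolved prior carfilzomib toxicities to grade 1 or better". Carfilzomib need not be the latest therapy, because the patient must have "previously failed carfilzomib at any point".

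**Blood counts at entry.** In Inclusion 9, ANC and WBC must be reached without growth factors within 1 week of starting treatment, and hemoglobin without red cell transfusion within 2 weeks. The platelet line asks for at least 100,000 cells/mm³ "for patients who have bone marrow plasmacytosis of <50%, or platelets" of at least 50,000 when plasmacytosis is 50% or more. It names no interval free of platelet transfusion. Appendix A has the same text.

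**DLT definitions.** Section 5.7(d) lists "Grade 4 thrombocytopenia, or Grade 3 thrombocytopenia with bleeding, or any requirement for platelet transfusion", for events in cycle 1. Section 5.7(e), on anemia, excepts what the underlying disease explains; item (d) has no such exception. Section 10.1 gives a second definition, restricted to treatment-related unmanageable toxicity that delays or ends treatment in cycle 1. Neither section refers to the other.

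**The concern.** A recovery rule should apply most firmly to the most recent drug. Read literally, this one does the reverse: unresolved grade 2 toxicity from a drug given five weeks ago excludes the patient, while the same toxicity from a drug given 22 days ago does not. Such a patient then starts a combination for which the protocol itself expects compounding toxicity.

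The platelet line raises a different problem. A patient whose count reaches the threshold only after a transfusion qualifies. If that patient needs another transfusion in cycle 1, section 5.7(d) records a DLT, whether or not cabozantinib contributed.

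Cohorts hold three to six patients, so one such event can decide a dose level. At 20 mg there is no lower level, and section 8.1.4 halts the study for unacceptable toxicity there. At a higher level, the result would be a lower dose carried into Phase II.

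**Working it through.** **Step 1: the plan's own figure.** Section 5.7 gives a Phase I size of 3 to 18. One cohort of 3 at the first level gives the minimum, and 3 levels × 6 patients = 18 gives the maximum. Both reproduce, and nothing proposed here changes them.

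**Step 2: the recovery gap.** Exclusion 1 starts at 4 weeks and Inclusion 6 permits entry at 3 weeks, so the uncovered interval is 4 − 3 = 1 week. How much of it Inclusion 4 closes depends on the reading:

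- Inclusion 4 read broadly covers toxicity from the carfilzomib-containing regimens it names.
- Section 5.7 limits the same requirement to carfilzomib toxicities.
- On either reading, a later drug given outside those regimens is not covered, and failure of carfilzomib at any point makes such a drug possible.

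**Step 3: from the gap to a DLT.** Section 5.7(a) needs grade 3 or higher, and DLTs are events that occur in cycle 1. Section 9 defines treatment-emergent events by onset or worsening after the first dose. A stable grade 2 event at entry therefore does not count; it has to worsen.

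**Step 4: from the platelet line to a DLT.** Under 5.7(d) the transfusion requirement is itself the event, so no worsening from baseline has to be shown. Under 10.1 a transfusion need judged unrelated to treatment would not count. However, 10.1 does not say which attribution levels qualify, and section 9.1.2 calls an event possibly related even when other causes explain it equally well, provided the timing fits.

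**Step 5: size, as illustration only.** The documents give neither a DLT rate nor a carry-over rate, so both are assumed. Under the standard 3+3 rule a level is cleared with 0 of 3, or with 1 of 3 followed by 0 of the next 3. With per-patient probability p and q = 1 − p:

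P(clear) = q³ + 3pq²·q³ = q³ + 3pq⁵

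True rate 20%, carry-over added in percentage points:

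- +0: p = 0.20, 0.512 + 0.197 = 0.709
- +2: p = 0.22, 0.475 + 0.191 = 0.665 (from unrounded terms)
- +5: p = 0.25, 0.422 + 0.178 = 0.600
- +10: p = 0.30, 0.343 + 0.151 = 0.494

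True rate 15%, +10 points: 0.814 falls to 0.600.

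If instead one of the first three patients is certain to count, for example because of platelet transfusion dependence at entry, the other two and the next three must all be free of DLT. P(clear) is then q⁵: 0.8⁵ = 0.328 against 0.709 at a 20% rate, and 0.9⁵ = 0.590 against 0.906 at 10%.

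Section 10.2 words the MTD rule as one of three or two of six patients with DLTs, which is ambiguous. The standard rule is assumed here.

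**The case against.** The strongest reply is section 10.1. If that definition governs, toxicity attributed to an earlier drug or to the myeloma is not a DLT, and a platelet transfusion is not a criterion in itself. This stands as far as it goes, but nothing gives 10.1 precedence over 5.7, and its attribution threshold is unstated.

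The second reply is that other criteria narrow the recovery gap. Entry also requires marrow, hepatic, renal and cardiac minimums, limits on QTcF and on PT/PTT, and no active infection. Section 5.2.2 repeats counts and chemistry within three days of day 1. This stands: what remains is mainly toxicity that these tests do not capture, from a drug outside the Inclusion 4 regimens, last given 3 to 4 weeks before. It does not answer the platelet point, because a recently transfused patient can pass the repeat count.

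The third reply is that nobody can say from the documents how many entrants fall in either gap. That is correct, and it is why only a range of assumed increments is shown.

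A reader might go further and infer that carry-over toxicity will be charged to cabozantinib and that the MTD will come out too low. The documents do not support that. It would require section 5.7 to prevail over 10.1, baseline grade 2 events to count without worsening, and a number of affected patients that is nowhere given.

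**Conclusion.** The point holds as two linked drafting gaps of moderate weight. The mismatch between 3 and 4 weeks is certain from the text; its effect is mainly on patient safety and on consistency between Exclusion 1, Inclusions 4 and 6, and section 5.7. The missing platelet window is equally certain, and it leads directly to a DLT if section 5.7(d) applies as written.

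The size is unknown. At a 20% true rate, assumed carry-over of 2 to 10 points costs about 4 to 21 percentage points of the chance of clearing a level. These figures rest on the standard 3+3 rule, on the assumed rates, and on carry-over events being counted as DLTs. They show that small cohorts are sensitive to such events; they do not forecast a bias.

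**What to change.** 1. **Recovery rule.** Reconcile Exclusion 1, Inclusions 4 and 6, section 5.7 and Appendix A, so that recovery to grade 0-1 also applies to agents permitted by the 3-week washout. Deleting the time qualifier from Exclusion 1 would do this. State whether Inclusion 4 means all toxicity of the listed regimens or that of carfilzomib alone.
2. **Platelet criterion.** In Inclusion 9 and Appendix A, add a transfusion-free condition to the platelet line, as the hemoglobin line already has. The sponsor should set the interval.
3. **DLT definition.** Merge sections 5.7 and 10.1 into one definition. It should say which attribution levels count and how cytopenia that is present at baseline or due to the disease is handled. The entry criterion alone is not enough: a patient admitted untransfused at 50,000 with heavy marrow involvement may still need a disease-related transfusion, which 5.7(d) would count.

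The cost is a few phrases in the criteria, the checklist and the DLT text. A few patients would wait longer or be screened out. The Phase I range of 3 to 18 is unchanged.
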